# 4.13 Determination of Sample Size

A total of 119 evaluable participants per arm will provide 80% power to detect a 30% placebo adjusted change from baseline in UACR at 12 weeks, assuming a standard deviation of 1.0 on the natural log-scale and  $\alpha$ =0.05. To account for approximately 5% drop-out, approximately 500 participants will be randomly assigned to study intervention (125 participants per group) such that approximately 476 evaluable participants (119 per group) complete the study.

### 4.14 Changes in the Conduct of the Study or Planned Analysis

No changes in the Conduct of the study or Planned analysis are included in the SAP, however a clarification is needed:

The expression at 12 weeks in the protocol refers to the end of 12 weeks of study treatment and it should be considered equal to the start of week 13 i.e. 12 weeks (end of 12 weeks treatment) refers to week 13 (starting of week 13). To have consistency along the SAP the expression at Visit 10 was considered in the description of the efficacy evaluation (section 4.10). However, the expression at 12 weeks was maintained for the description of some endpoints accordingly to the protocol.

The first baseline eGFR category was reported in the shells as <30 to also include the patients with an eGFR between 20 and 30 based on the CSP and patient with an eGFR less than 20.

TP-GDO-WW-016-08 Effective Date: 26 Nov 19 Project Document Effective Date: Date of last signature Related to: SOP-GDO-WW-019 Page 37 of 50

# 6 APPENDICES

TP-GDO-WW-016-08 CONFIDENTIAL Project Document Version No. 3.0 Effective Date: 26 Nov 19 Project Document Effective Date: Date of last signature Related to: SOP-GDO-WW-019 Page 39 of 50

Appendix A: Schedule of Activities

	Pre-		ò	Pre-	Baseline/								3	
Procedure	scree	Screeni	Start Pun-in	rando-	Rando			Treatment Period	ent Per	iod		EOT/ET a	Salety	Notes
	ning	56 11	III-IIII	misation	misation								dn-wono i	
Visit b	Opti onal	1a	1b	2	3	4	2	9	7	%	6	10	11	
	3	8-)	(-7	-1										
Week		to -7)*	to -6)*		-	-	7	3	4	7	10	13	17	* Applies to
		-6 to -5	-5 to -4											SGLT2i naïve
Day	о	95-)	(-49	-10 to -3	1	3	8 ±2	15	22	43	64 ±3	82	113	patients
		to -49)*	to -42)*			<del>+</del> 1		Ħ	#3	#3		#3	#	
		-42	-35 to -28											
		to -35												
Informed consent	X	X												
Local laboratory														Sample
urine samples for	×													according to
albumin and	<													local clinical
creatinine														practice.
Inclusion and		Λ	>		Λ									
exclusion criteria		<	<		<									
Enrolment in		>												
RTSM		<												
Demography,														
height, smoking		>												
history, alcohol		ζ.												
consumption														
Physical					Δ. (200)									Ton oito michita
examination,		×			Apre)							×	×	rol suc visits
weight					(peop									omy.
Medical/ surgical		Λ			Λ									
history		<			<									
Concomitant		X		X	X	X	X	X	X	X	X	X	X	
IIICAICAIOII														

Project Document Version No. 2.0 Project Document Effective Date: Date of last signature Page 40 of 50

Procedure	Pre- scree ning	Screeni	Start Run-in	Pre- rando- misation	Baseline/ Rando misation			Treatment Period	ent Per	iod		EOT/ET a	Safety Follow-up	Notes
Visit b	Opti onal	1a	1B	2	ဧ	4	v	9	7	∞	6	10	11	
Week	o o	(-8 to -7)* -6 to -5	(-7 to -6)* -5 to -4	-1	1	н	2	က	4	7	10	13	17	* Applies to SGLT2i naïve
Day	o o		(-49 to -42)* -35 to -28	-10 to -3		£ ± 1	8 ±2	15 ±3	22 ±3	43 ±3	64 ±3	88 #3	113	patients
Adverse events		SAEs		SAEs only	×	×	×	×	×	×	×	X	X	
Vital signs (blood pressure, pulse rate)		×			X (predose)	×	×	×	×	×	×	×	×	Background treatment for hypertension should be individually optimised and stable for 3 weeks before randomisation (Visit 3); BP assessed for eligibility at Visit 3.
Digital 12-lead safety ECG		X d			X (pre- dose)	×		X		×		X		ECGs to be added as clinically indicated.
Local echocardio- graphy		X d												Needed to confirm eligibility if not assessed in past 12 months

Procedure	Pre- scree ning	Screeni	Start Run-in	Pre- rando- misation	Baseline/ Rando misation			Treatm	Treatment Period	po		EOT/ET a	Safety Follow-up	Notes
Visit b	Opti onal	1a	1b	2	3	4	2	9	7	8	6	10	11	
Week	o o	(-8 to -7)* -6 to -5	(-7 to -6)* -5 to -4	-1	1	1	7	æ	4	7	10	13	17	* Applies to SGLT2i naïve
Day	S	(-56 to -49)* -42 to -35	(-49 to -42)* -35 to -28	-10 to -3	-	£ #	8 ±2	15 £3	£3 23	£3 £3	64 ±3	88 #3	113	patients
Local laboratory blood samples for clinical chemistry and haematology		p X												
Local laboratory urine sample for albumin, creatinine, and urinalysis		p X												Spot urine sample
Local laboratory blood sample for NT-proBNP		p X												
Local laboratory blood sample for FSH measurement		y X												To confirm postmenopausal status of women (only women of non-child-bearing potential will be included in the study).
Local laboratory RT-PCR test for SARS-CoV-2				X										Optional. If available at site.

TP-GDO-WW-016-08 Effective Date: 26 Nov 19 Related to: SOP-GDO-WW-019

CONFIDENTIAL

Project Document Version No. 2.0 Project Document Effective Date: Date of last signature Page 42 of 50

Visit b         Opti onal onal onal onal onal onal celebrates         1a           Week         (-8 to -7)*           Day         (-56 to -5 to -40)*           Local laboratory         to -35           serum/plasma         to -35           Local laboratory         serum/plasma           serum/plasma         samples for K+           and Na+         creatinine           including eGFR         calculation           Central         laboratory blood		rando- misation	Rando misation			l reatin	Freatment Period	iod		EOT/ET a	Follow-up	Notes
k  laboratory  n/plasma  eles for K + Na + Il laboratory  n/plasma  oles for  inine  ding eGFR  ilation  ral  ratory blood	1b	2	3	4	2	9	7	8	6	10	11	
k  Il laboratory  m/plasma  oles for K + Na + Il laboratory  m/plasma  oles for  inine  ding eGFR  ilation  ral	(-2	-1										
ul laboratory n/plasma oles for K + Na + Il laboratory n/plasma oles for inine ding eGFR ilation ral	to -6)*		1		7	e	4	_	10	13	17	* Applies to
ul laboratory n/plasma sles for K + Na + Il laboratory n/plasma n/plasma sles for inine dding eGFR ral	-5 to -4											SGLT2i naïve
boratory lasma for K + boratory lasma for g eGFR ion	(-49	-10 to -3	1	3	8 ±2	15	22	43	64 ±3	82	113	patients
boratory lasma for K + boratory lasma for e g eGFR ion	to -42)*			#		#3	#3	#3		#3	#	
Local laboratory serum/plasma samples for K + and Na + Local laboratory serum/plasma samples for creatinine including eGFR calculation Central laboratory blood	-35 to -28											
serum/plasma samples for K + and Na + Local laboratory serum/plasma samples for creatinine including eGFR calculation Central												Results needed for eligibility
samples for K.  and Na + Local laboratory serum/plasma samples for creatinine including eGFR calculation Central laboratory blood		×	×	×	×	×	×	×	×	×		and to assess
Local laboratory serum/plasma samples for creatinine including eGFR calculation Central												criteria at each
serum/plasma samples for creatinine including eGFR calculation Central												
samples for creatinine including eGFR calculation Central												
creatinine including eGFR calculation Central laboratory blood			>	>	>	×	>	>	>	>		
including eGFR calculation Central laboratory blood			<	<	<	<	<	<	<	<		
calculation Central laboratory blood												
Central laboratory blood												
laboratory blood												
samples for												
clinical			V (mro									
chemistry and			-21d) V	×	×	×	×	×	×	×	×	
haematology;			(ason									
and plasma												
sample for K +												
measurement												

Procedure	Pre- scree ning	Screeni	Start Run-in	Pre- rando- misation	Baseline/ Rando misation			Treatment Period	ent Per	iod		EOT/ET a	Safety Follow-up	Notes
Visit b	Opti onal	1a	1b	2	3	4	9	9	7	8	6	10	11	
	3	8-)	L -)	-										
Week		to -7)*			1	1	7	က	4	7	10	13	17	* Applies to
		-6 to -5	_											SGLT2i naïve
Day	3	95-)	(-49	-10 to -3	1	3	2 ∓8	15	22	43	64 ±3	58	113	patients
			to -42)*			#		Ħ	<del>+</del> 3	#3		#3	#	
			-35 to -28											
		to -35												
Central														
laboratory serum														
sample for				×										
creatinine for														
eGFR calculation														
Central														
laboratory serum					X (nre-									
sample for				×	-Vigiro-	×	×	×	×	×	×	×	×	
cystatin C for					(ason									
eGFR calculation														
Central														
laboratory blood														A flor at least
samples for					X (pre-							Þ	Þ	o home feeting
HbA1c,					dose)							<	<	6-110th Tasting
cholesterol, and														roi irpids.
lipids														
Central					A (me)									
laboratory					-old) v					×		×	×	
urinalysis					(ason									
1														

Procedure	Pre- scree ning	Screeni	Start Run-in	Pre- rando- misation	Baseline/ Rando misation		-	Treatm	Treatment Period	iod		EOT/ET a	Safety Follow-up	Notes
Visit b	Opti onal	1a	1b	2	8	4	v	9	7	∞	6	10	11	
Week	3	(-8 to -7)* -6 to -5	(-7 to -6)* -5 to -4	1-	1	1	2	8	4	7	10	13	17	* Applies to SGLT2i naïve
Day	၁	(-56 to -49)* -42 to -35	(-49 to -42)* -35 to -28	-10 to -3	-	3 ±1	8 ±2	15 ±3	22 ±3	43 ±3	64 ±3	85 ±3	113 ±4	patients
Central laboratory urine samples for albumin, creatinine (for UACR calculation), Na + , K + , uric acid, urea, osmolality, glucose, and cortisol f  Pharmaco- kinetics  Predose sample for AZD9977 and dapagliflozin plasma concentrations				X e. f			×		×	×	×	×	×	First morning void urine sample collected at home in provided vials over 3 consecutive days until the visit day.  Collected before dose intake at site, or 1 day after last dose for the EOT/ET visit.
Optional postdose plasma samples for AZD9977 and dapagliflozin concentrations									×					Collected at 1 (±0.25), 2 (±0.25), 4 (±0.5), and 6 (±1) hours postdose.

TP-GDO-WW-016-08 Effective Date: 26 Nov 19 Related to: SOP-GDO-WW-019

CONFIDENTIAL

Project Document Version No. 2.0
Project Document Effective Date: Date of last signature
Page 45 of 50

	Pre-	Screeni	Start	Pre-	Baseline/				-	7		FELLE	Safety	2070
rroceaure	scree ning	ng	Run-in	rando- misation	Kando misation			ı reaum	ı reatment reriod	D 0		EQ1/E1 ::	Follow-up	Salovi
Visit b	Opti onal	1a	1b	2	3	4	v	9	7	∞	6	10	11	
Week	၁	(-8 to -7)*	(-7 to -6)*	-1	1	1	2	က	4	7	10	13	17	* Applies to
		-6 to -5	-5 to -4											SGLT2i naïve
Day	J	99-)	(-49	-10 to -3	1	e	8 ±2	15	22	43	64 ±3	82	113	patients
		to -49)*	to -42)*			#		#3	#3	∓3		#3	#	
		-42	-35 to -28											
		to -35												
Pharmaco-														
dynamics														
(Central														
laboratory)														
Blood samples														Colland at the
for NT-proBNP,														collected at the
aldosterone,					X (nre-									day
renin, ACTH,					-Vigit X		×		×			×	×	day. After at least
cortisol,					(Decon									8-bour fasting
copeptin, and														for FPG
FPG														101 11 0.
Exploratory														
measurements														
and biomarkers														
Serum/plasma														
samples for					X (pre-				>			×	>	Central
cardiovascular					(ose)				ζ.			\$	4	laboratory.
biomarkers														
Optional serum,														
plasma, and														
urine samples for					X (pre-				>			>		
exploratory					(esop				<			<		
assessment of														
biomarkers														
										1				

TP-GDO-WW-016-08 Effective Date: 26 Nov 19 Related to: SOP-GDO-WW-019

CONFIDENTIAL

Project Document Version No. 2.0 Project Document Effective Date: Date of last signature Page 46 of 50

Procedure	Pre- scree ning	Screeni	Start Run-in	Pre- rando- misation	Baseline/ Rando misation			Treatm	Treatment Period	poi		EOT/ET a	Safety Follow-up	Notes
Visit b	Opti onal	1a	1b	2	ဗ	4	v	9	7	«	6	10	11	
Week	o o	(-8 to -7)*	(-7 to -6)*	-1	1	1	2	က	4	7	10	13	17	* Applies to
		-6 to -5	-5 to -4											SGLT2i naïve
Day	3	95-)	(-49	-10 to -3	1	3	8 ±2	15	22	43	64 ±3	85	113	patients
		to -49)*	to -42)*			#		Ħ	#3	#3		#3	#	
		-42 to -35	-35 to -28											
Optional														
genetic sample														
for Genomics					X (pre-									
Initiative					dose)									
exploratory														
analysis														
Study														
treatments											•			
Randomisation in RTSM					×									
Dapagliflozin 10 mg			Daily-(morning) self-administratio	Daily-(morning) self-administration								Daily-(morning) self administration a	ning) self ration a	
														Taken at the site
Study treatment					Daily (r	normin	Daily (moming) self-administration of the assigned study treatment	elfadministratic study treatment	ration o	f the ass	igned			on visit days, after completing all predose procedures.
Drug dispensation			×		×				×	×	×	X		•
Drug accountability					×	×	×	×	×	×	×	X	×	

RTSM=Randomisation and Trial Supply Management, SAE=serious adverse event; SARS-CoV-2=severe acute respiratory syndrome coronavirus 2; UACR=urinary albumin ACTH=adrenocorticotropic hormone; BP=blood pressure; BUN=blood urea nitrogen; CKD=chronic kidney disease; CSP=Clinical Study Protocol; ECG=electrocardiogram; eGFR=estimated glomerular filtration rate; EOT=end of treatment; ET=early termination; FPG=fasting plasma glucose; FSH=follicle stimulating hormone; HbA1c=glycated haemoglobin; HF=heart failure; K+=potassium; Na+=sodium; NT-proBNP=N-terminal natriuretic peptide; RT-PCR=reverse transcriptase polymerase chain reaction; to creatinine ratio.

Note: Visits at Week 7 and Week 13 (Visits 8 and 10) correspond to visits after completion of 6 weeks and 12 weeks of study treatment, respectively.

- Patients will continue on open label dapagliflozin 10 mg after the EOT visit during the safety follow up period up to Visit 11. Patients who discontinue study treatment early may continue on open label dapagliflozin 10 mg after the ET visit during the safety follow up period up to Visit 11, as judged by the investigator. Patients who
  - If site visits are not possible due to local SARS-CoV-2 restrictions, home nursing visits may be considered after discussion with and approval by the Sponsor withdraw consent may perform an ET visit but the safety follow-up will not be performed
    - c Week and day for pre-screening will be at the discretion of the investigator.
- Results from the screening tests are needed to confirm eligibility before the run-in period can start.
- Results are needed to confirm eligibility before randomisation. Serum/plasma Na+ will be assessed at Visit 2 only. The eGFR-based participant stratification will rely on central eGFR assessment at Visit 2.

Related to: SOP-GDO-WW-019

### Appendix B: eGFR calculation formulas

The participant's eGFR (mL/min/1.73 m²) will be calculated based on the standard BSAadjusted CKDEPI formula using serum/plasma creatinine concentration alone (Levey et al 2009) as measured at a local laboratory and using both serum creatinine and serum cystatin C concentrations (Inker et al 2012) at a central laboratory. Note that for eGFR calculation based on creatinine levels, the calibrated methods provide equivalent results for plasma and serum sample types.

eGFR calculation using standard BSA-adjusted CKD-EPI formula using serum/plasma creatinine concentration (Levey et al 2009):

$$eGFR \ (mL/min/1.73m^2) = 141 \times min \ (SCr/\kappa, 1)^{\alpha} \times max \ (SCr/\kappa, 1)^{-1.209} \times 0.993^{Age} \times [1.018 \ if female] \times [1.159 \ if black]$$

 $\kappa$  is 0.7 for females and 0.9 for males,  $\alpha$  is -0.329 for females and -0.411 for males, min indicates the minimum of SCr/ $\kappa$  or 1, and max indicates the maximum of SCr/ $\kappa$  or 1. eGFR calculation using standard BSA-adjusted CKD-EPI formula using both serum creatinine and serum cystatin C concentrations (Inker et al 2012):

$$eGFR$$
 (mL/min/1.73m²) = 135 × min(SCr/ $\kappa$ , 1)a × max(SCr/ $\kappa$ , 1)-0.601 × min(Scys/0.8, 1)-0.375 × max(Scys/0.8, 1)0.711 × 0.995Age × 0.969 [if female] × 1.08 [if black]

SCr (serum creatinine) = mg/dL, Scys (standardised serum cystatin C) = mg/L,  $\kappa=0.7$  (females) or 0.9 (males),  $\alpha=$  -0.248 (females) or -0.207 (males), min(SCr/ $\kappa$  or 1) = indicates the minimum of SCr/ $\kappa$  or 1, max(SCr/ $\kappa$  or 1) = indicates the maximum of SCr/ $\kappa$  or 1, min(Scys/0.8, 1) = indicates the minimum of Scys/0.8 or 1, max(Scys/0.8, 1) = indicates the maximum of Scys/0.8 or 1, age = years

TP-GDO-WW-016-08 Effective Date: 26 Nov 19 Related to: SOP-GDO-WW-019

**Project Document Effective Date**: Date of last signature Page 49 of 50

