Week	c	(-8 to -7)* -6 to -5	(-7 to -6)* -5 to -4	-1	1	1	2	3	4	7	10	13	17	* Applies to SGLT2i naïve	For details on run-in period see
Day	c	(-56 to -49)* -42 to -35	(-49 to -42)* -35 to -28	-10 to -3	1	3 ± 1	8 ±2	15 ±3	22 ±3	43 ±3	64 ±3	85 ±3	113 ±4	patients	Section 4.1
Study treatment					Daily (m	ornin		adminis ly treatr		of the a	ssigned			Taken at the site on visit days, after completing all predose procedures.	Sections 4.1, 6.2, 6.4
Drug dispensation			Х		Х				Х	Х	Х	Х			Sections 6.2, 6.3, and 6.4
Drug accountability					Х	Х	Х	Х	Х	Х	Х	Х	Х		Sections 6.2, 6.4

ACTH=adrenocorticotropic hormone; BP=blood pressure; BUN=blood urea nitrogen; CKD=chronic kidney disease; CSP=Clinical Study Protocol; ECG=electrocardiogram; eGFR=estimated glomerular filtration rate; EOT=end of treatment; ET=early termination; FPG=fasting plasma glucose; FSH=follicle stimulating hormone; HbA1c=glycated haemoglobin; HF=heart failure; K⁺=potassium; Na⁺=sodium; NT-proBNP=N-terminal natriuretic peptide; RT-PCR=reverse transcriptase polymerase chain reaction; RTSM=Randomisation and Trial Supply Management, SAE=serious adverse event; SARS-CoV-2=severe acute respiratory syndrome coronavirus 2; UACR=urinary albumin to creatinine ratio.

Note: Visits at Week 7 and Week 13 (Visits 8 and 10) correspond to visits after completion of 6 weeks and 12 weeks of study treatment, respectively.

- ^a Patients will continue on open label dapagliflozin 10 mg after the EOT visit during the safety follow up period up to Visit 11. Patients who discontinue study treatment early may continue on open label dapagliflozin 10 mg after the ET visit during the safety follow up period up to Visit 11, as judged by the investigator. Patients who withdraw consent may perform an ET visit but the safety follow-up will not be performed.
- ^b If site visits are not possible due to local SARS-CoV-2 restrictions, home nursing visits may be considered after discussion with and approval by the Sponsor.
- ^c Week and day for pre-screening will be at the discretion of the investigator.
- ^d Results from the screening tests are needed to confirm eligibility before the run-in period can start.

e Results are needed to confirm eligibility before randomisation. Serum/plasma Na⁺ will be assessed at Visit 2 only. The eGFR-based participant stratification will rely on central eGFR assessment at Visit 2.

Clinical Study Protocol - 7.0 AZD9977 and dapagliflozin - D6402C00001

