NOTE: For the optional pre-screening visit there is a separate informed consent. Refer to Section 4.1.1.

14 Provision of signed and dated written Optional Genetic Research Information informed consent prior to collection of samples for optional genetic research that supports Genomic Initiative.

Participants are eligible to be randomised in the study only if all of the following criteria apply at randomisation (Visit 3):

15 $eGFR \ge 30 \text{ mL/min}/1.73 \text{ m}^2$ (by CKD-EPI formula at central laboratory) based on results from pre-randomisation Visit 2.

Note: Recruitment will start with patients who have $eGFR \ge 30 \text{ mL/min}/1.73 \text{ m}^2$. During the study, the Safety Unblinded Data Review Committee may decide to also include patients with $eGFR \ge 20$ to $< 30 \text{ mL/min}/1.73 \text{ m}^2$

- 16 UACR \geq 30 mg/g (3 mg/mmol) and < 3000 mg/g (300 mg/mmol) based on central laboratory samples collected at pre-randomisation Visit 2. Refer to Section 8.1.1.
- 17 Serum/plasma K⁺ level \geq 3.5 and < 5.0 mmol/L within 10 days prior to randomisation (Visit 3) from local laboratory.
- 18 Serum/plasma sodium (Na⁺) level within normal reference values within 10 days prior to randomisation (Visit 3) from local laboratory.
- 19 Systolic BP ≥ 90 and < 150 mmHg (or < 180mmHg if the patient is already receiving 3 or more antihypertensive drugs) at randomisation (Visit 3), with no change to antihypertensive treatments in previous 3 weeks. Antihypertensive drugs include, but are not limited to, a diuretic, ACEI, ARB, beta-blocker and calcium channel blocker.

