8.2.4 Clinical Safety Laboratory Assessments

Blood and urine samples for determination of clinical chemistry, haematology, and urinalysis will be taken at the visits indicated in the SoA.

Additional safety samples may be collected if clinically indicated at the discretion of the investigator. The date, time of collection, and results (values, units, and reference ranges) will be recorded on the appropriate eCRF.

The clinical chemistry, haematology, and urinalysis will be performed at a local laboratory for screening, and at a central laboratory at baseline and subsequent visits, as indicated in the SoA.

Measurement of electrolytes (Na⁺ and K⁺) and creatinine at local laboratories may be done on either plasma or serum samples, depending on their capabilities, while these measurements at the central laboratory will be done on serum samples. In addition, K⁺ levels will be measured in plasma samples at the central laboratories for exploratory analysis.

The participant's eGFR (mL/min/1.73 m²) will be calculated based on the standard BSA-adjusted CKD-EPI formula using serum/plasma creatinine concentration alone (Levey et al 2009) as measured at a local laboratory and using both serum creatinine and serum cystatin C concentrations (Inker et al 2012)at a central laboratory. Note that for eGFR calculation based on creatinine levels, the calibrated methods provide equivalent results for plasma and serum sample types.

eGFR calculation using standard BSA-adjusted CKD-EPI formula using serum/plasma

creatinine concentration (Levey et al 2009):

$eGFR (mL/min/1.73m^2) = 141 \times min (SCr/\kappa, 1)^{a} \times max (SCr/\kappa, 1)^{-1.209} \times 0.993^{Age} \times [1.018 if female] \times [1.159 if black]$

 κ is 0.7 for females and 0.9 for males, α is -0.329 for females and -0.411 for males, min indicates the minimum of SCr/ κ or 1, and max indicates the maximum of SCr/ κ or 1.

eGFR calculation using standard BSA-adjusted CKD-EPI formula using both serum creatinine and serum cystatin C concentrations (Inker et al 2012):

$eGFR (mL/min/1.73m^2) = 135 \times min(SCr/\kappa, 1)^{a} \times max(SCr/\kappa, 1)^{-0.601} \times min(Scys/0.8, 1)^{-0.375} \times max(Scys/0.8, 1)^{0.711} \times 0.995^{Age} \times 0.969$ [if female] $\times 1.08$ [if black]

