contributed to hyperkalaemia; and/or continuation with reassessment; or permanent discontinuation.

- If the repeat local laboratory sample has serum/plasma $K^+ \le 5.5 \text{ mmol/L}$, then study treatments can be resumed, even if the central laboratory sample has serum $K^+ > 6.0 \text{ mmol/L}$.

If the investigator is aware of any change in the participant's clinical status that may influence serum electrolyte levels or fluid balance (eg, vomiting and/or diarrhoea > 1 day), it is recommended to reassess serum/plasma K^+ levels as soon as possible after the acute event. In case of permanent discontinuation, serum/plasma K^+ levels should be monitored until resolution or stabilisation.

F 2 Deterioration of Renal Function

Serum creatinine will be measured both at a local laboratory and a central laboratory at all baseline and on-treatment visits according to the SoA. Repeat samples should be sent for both central and local laboratory assessment. It is expected that local laboratory results will be available prior to central laboratory results. As local and central laboratories will calculate eGFR using different formulas, central eGFR values should always be compared to central eGFR values and local eGFR values should always be compared to local eGFR values. For local laboratories, the eGFR assessment at Visit 3 (prior to the start of study treatment) will be taken as the baseline eGFR value.

- If eGFR shows a 30-50% decline from baseline and an absolute value ≥ 15 mL/min/1.73 m² (based on local and/or central laboratory samples), eGFR should be reassessed within 1 week.
 - If persistent 30-50% decline stabilises upon weekly follow-ups, eGFR monitoring may return to the standard SoA, at investigator's discretion.
- If eGFR shows a >50% decline from baseline and/or decreases to an absolute value < 15 ml/min/1.73 m² (based on local and/or central laboratory samples), eGFR should be reassessed within 48 hours.
 - If eGFR shows a 30% to 50% decline from baseline and an absolute value $\geq 15 \text{ mL/min/1.73 m}^2$, eGFR should be reassessed within 1 week.
 - If eGFR again shows a >50% reduction from baseline and/or absolute value
 <15 mL/min/1.73 m², study treatments must be discontinued immediately and eGFR should be followed up within a week and weekly until signs of improvement and stabilisation.

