### Deteriorating renal function related safety topics of interest

- Number (%) of patients with a decrease in eGFR of  $\geq 25\%$ ,  $\geq 30\%$ ,  $\geq 40\%$  and  $\geq 57\%$ from baseline at any visit during the randomized treatment period (based on central lab values). These decreases would need to be confirmed by another central eGFR measure. Summary will be based on the on-treatment definition included in section 4.11.2
- Number (%) of patients who met the protocol mandated renal discontinuation criteria in the study:
  - At any visit during the randomized treatment period eGFR >50% decline from baseline and/or decrease to an absolute value <15 ml/min/1.73 m^2 confirmed with eGFR >50% decline from baseline and/or decrease to an absolute value <15 ml/min/1.73 m^2 (based on central lab values).

Confirmation has to be the next consecutive central lab sample which is  $\leq 14$  days of the original central lab sample.

Additional analysis will include eGFR lab values confirmed at the next consecutive central lab sample regardless of time from initial lab sample.

- Number (%) of patients with >25% residual decrease in eGFR at safety follow-up visit compared to baseline
- Number (%) of patients who discontinued due to meeting the protocol mandated renal discontinuation criteria in the study

†Based on the end of treatment CRF page

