- eGFR (mL/min/1.73 m^2) will be calculated using the BSA adjusted CKD-EPI formula and including both serum creatinine and serum cystatin C for central laboratory assessments, and with serum/plasma creatinine alone for local laboratory assessments. Extended formulas adopted for eGFR calculation are provided in Appendix B.
- The post-randomisation INR measurements may be done at a local laboratory if the necessary material provided by the central laboratory is not available; and the measurements may be omitted if the local laboratory is not capable of doing the measurements. Refer to Laboratory Manual for details.
- These tests are not required at screening or pre-randomization.
- g Per Friedewald equation
- h Central laboratory for all cystatin C measurements.

Laboratory parameters will be presented for each treatment group and/or visit.

The outlier laboratory values based on predefined criteria will be presented by treatment as defined in Table 3. A laboratory value will be considered abnormal if it meets the predefined criteria for the abnormality, except where the baseline value met the criteria for the abnormality and the new value is less extreme than the baseline value. Only the most severe value per participant will be accounted for.

Table 3 Laboratory abnormalities by predefined criteria

Blood Chemistry						
ALP Number of subjects with any on-treatment value >1.5x ULN >3x ULN	Total bilirubin  Number of subjects with any on-treatment value  >1.5x ULN  >2x ULN					
ALT Number of subjects with any on-treatment value >3x ULN >5x ULN >10x ULN >20x ULN	Na + (mmol/L)  Number of subjects with any on-treatment value  <120  <130  >150					

Blood Chemistry						
AST Number of subjects with any on-treatment value >3x ULN >5x ULN >10x ULN >20x ULN	K + (mmol/L)  Number of subjects with any on-treatment value ≤2.5					
ALT or AST  Number of subjects with any on-treatment value  >3x ULN  >5x ULN  >10x ULN  >20x ULN						
Haematocrit						
Haematocrit (Vol)  Number of subjects with any on-treatment value <0.20 >0.55 >0.60	Hemoglobin (g/L) Number of subjects with any on-treatment value <60 >180 >200					

For each scheduled post-baseline visit, descriptive statistics for all clinical chemistry and haematology parameters will be presented for observed values at each visit (including baseline) and change from baseline.

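### The creatinine–cystatin C eGFR equation is printed in both documents with +0.711 instead of −0.711 on cystatin C; used as printed, it overstates eGFR and hardly registers renal decline.

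*SAP*

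**What the plan says.** Protocol 8.2.4 and SAP Appendix B give two eGFR equations. Local laboratories use creatinine alone; the central laboratory uses creatinine and cystatin C together.

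In the combined equation the term for cystatin C above 0.8 mg/L reads "max(Scys/0.8, 1) 0.711" in the SAP and "max(Scys/0.8, 1)^{0.711" in the protocol, so the exponent is +0.711 in both. The term for cystatin C below 0.8 mg/L, printed just before it, is "min(Scys/0.8, 1) -0.375" in the SAP. The creatinine exponents are also negative: −0.601 above κ, and −0.248 (women) or −0.207 (men) below it.

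The SAP treats this text as a specification. A footnote to its Table 2 says: "Extended formulas adopted for eGFR calculation are provided in Appendix B".

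Central eGFR is then used in several places:

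- Randomisation criterion 15 in Protocol 5.1 is assessed "by CKD-EPI formula at central laboratory) based on results from pre-randomisation Visit 2".
- Protocol 1.3, footnote e, states: "The eGFR-based participant stratification will rely on central eGFR assessment at Visit 2".
- SAP 4.11.3 counts eGFR falls of at least 25%, 30%, 40% and 57% on central values and adds: "These decreases would need to be confirmed by another central eGFR measure". Its count of patients who met the renal discontinuation criteria is also based on central values.
- Protocol Appendix F 2 compares central values only with central values, and gives the reason: "As local and central laboratories will calculate eGFR using different formulas".

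**The concern.** A rise in either marker should lower estimated GFR. With +0.711 the equation obeys this up to 0.8 mg/L of cystatin C and reverses above it. The error can therefore be seen inside the documents, without the cited source.

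If the printed form were programmed:

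- The lower eGFR bound of criterion 15 would exclude almost nobody.
- Nearly every patient would be placed in the ≥45 stratum and subgroup, although the protocol caps that group at 35% and asks for at least 20% with eGFR 20 to <30.
- The confirmed central declines in SAP 4.11.3 would be largely missed. Deteriorating renal function is one of the trial's three safety topics of interest.

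**Working it through.** Neither document gives a worked eGFR value, so there is no stated figure to reproduce. The check evaluates the equation as printed and again with −0.711, and compares both with the documents' creatinine-only formula. The documents give no marker values; those below are assumptions, for non-black patients.

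**Equations** (creatinine above κ, cystatin C above 0.8; κ = 0.9 for men, 0.7 for women)

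- Combined: 135 × (SCr/κ)^−0.601 × (Scys/0.8)^e × 0.995^age × 0.969 if female, with e = +0.711 as printed.
- Creatinine-only: 141 × (SCr/κ)^−1.209 × 0.993^age × 1.018 if female.

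**One patient: man, 70, SCr 1.8 mg/dL, Scys 1.8 mg/L**

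- Printed: 135 × 0.6593 × 1.7799 × 0.7041 = 111.5
- With −0.711: 135 × 0.6593 × 0.5618 × 0.7041 = 35.2
- Creatinine-only: 141 × 0.4326 × 0.6116 = 37.3

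The ratio of printed to negative form is (Scys/0.8)^(2 × 0.711) = (Scys/0.8)^1.422. It is 2.44 at 1.5 mg/L, 3.17 at 1.8 and 5.05 at 2.5. At or below 0.8 mg/L the two forms are identical.

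**Direction (man, 70, SCr 1.8)**

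| Scys (mg/L) | 0.6 | 0.8 | 1.0 | 1.5 | 2.0 | 3.0 |
|---|---|---|---|---|---|---|
| Printed | 69.8 | 62.7 | 73.4 | 98.0 | 120.2 | 160.4 |
| With −0.711 | 69.8 | 62.7 | 53.5 | 40.1 | 32.7 | 24.5 |

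**Response to decline when both markers agree.** For each reference eGFR, SCr is solved from the creatinine-only formula and Scys from the −0.711 form; the printed equation is then evaluated at that pair (man, 70).

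| Reference eGFR | 60 | 45 | 30 | 20 | 15 |
|---|---|---|---|---|---|
| Printed value | 105.0 | 105.2 | 105.4 | 105.7 | 105.8 |

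For a woman of 70 the printed value goes from 96.8 at 60 to 97.5 at 20. Over both sexes at ages 50, 70 and 80, and reference values from 60 to 20, the printed value is about 1.6 to 5.6 times too high. For the man, a fall from 40 to 24 (−40%) prints as +0.3%, and from 50 to 24 (−52%) as +0.4%.

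If both markers double, the printed value changes by 2^(0.711 − 0.601) − 1 = +7.9%; with the minus sign it changes by 2^(−0.711 − 0.601) − 1 = −59.7%.

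**Unequal changes.** The printed value falls only if log-creatinine rises more than 0.711/0.601 = 1.18 times as much as log-cystatin C. Going from 1.5/1.5 to 3.0/2.0 (SCr/Scys; man, 70) prints 109.3 to 88.4 (−19%), against 44.7 to 24.0 (−46%) with the minus sign.

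**Criterion 15 (man, 70, Scys 1.8).** A printed value below 30 needs creatinine above 16.0 mg/dL, where the creatinine-only eGFR is 2.7. A value below 45 needs creatinine above 8.2 mg/dL (creatinine-only eGFR 6.0).

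**The case against.** **The minus sign may have been lost when the PDFs were read.** Hyphens do drop out elsewhere in the text; the same SAP appendix has CKDEPI in one line and CKD-EPI a few lines later. The SAP repeats the protocol's wording, so agreement between the two is not fully independent evidence. This stands as a reason to look at the page. It is still the less likely explanation, because the sign is missing at the same place in both documents while the adjacent −0.601 and −0.375 keep theirs.

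**The laboratory probably uses the correct equation.** Both documents call the formula standard and cite its source. Values near 105 in patients screened locally at 60 or below would be noticed. This also stands: nothing shows that the printed form was programmed. But the SAP is what programmers and checkers work from, and text and citation would conflict with no rule for which governs.

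**The flat line is a constructed case.** It needs the two markers to move together. If creatinine alone rises, the percentage fall is the same under either sign (−34.1% for a doubling). That is correct, and the −19% path above shows a partial response.

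**Other safeguards remain.** Local eGFR uses the creatinine-only formula, limits entry at screening and can by itself trigger the actions in Appendix F 2. Serum creatinine, the renal preferred terms and the CRF-based count of renal discontinuations do not use this equation. These points limit the consequences. They do not protect criterion 15, the stratum or the central-laboratory decline counts.

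**Conclusion.** The concern holds. The exponent as printed is wrong on the documents' own evidence: it reverses the equation's direction at 0.8 mg/L and gives 111.5 where the creatinine-only formula gives 37.3. Used as printed, it would overstate eGFR roughly 1.6- to 5.6-fold over the trial's range of 60 to 20 and barely register a decline in which both markers rise together.

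Three limits apply. The sign has to be confirmed on the source pages. Every consequence depends on the printed form having been coded, which the documents do not show. The multipliers rest on assumed marker values, and the flat response on the two markers agreeing.

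Sample size and the UACR endpoint do not depend on the equation. In the primary model the eGFR stratum is only a covariate, so a wrong stratum costs balance and precision and does not by itself bias the randomised comparison. This should be fixed, but it does not undermine the primary analysis.

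**What to change.** 1. Check the exponent on the source page of Protocol 8.2.4 and SAP Appendix B. If it is +0.711 there, print −0.711 in both.
2. Obtain and file confirmation that the central laboratory and any SAS derivation use the negative exponent. A worked test value makes this quick: man, 70, non-black, SCr 1.8 mg/dL, Scys 1.8 mg/L should return 35.2, not 111.5.
3. Re-derive eGFR values or strata only if the printed form turns out to have been used.

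The cost is one character in each document and one check with the laboratory and the programmers.
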